9.8.1 Distinguishing intercurrent HIV infection from vaccine-induced positive serology

The study product may elicit an antibody response to HIV proteins. Therefore, vaccineinduced positive serology (VISP) may occur in this study. Several precautionary measures will be taken to distinguish intercurrent HIV infection from vaccine-induced positive serology. These precautionary measures include:

- Participants will have physical examinations at visits specified in Appendix H. Signs or symptoms of an acute HIV infection syndrome, an intercurrent illness consistent with HIV-1 infection, or probable HIV exposure would prompt a diagnostic workup per the HVTN algorithm for Recent Exposure/Acute Infection Testing to determine HIV infection.
- HIV testing will be performed at multiple timepoints throughout the study (see Appendix H). The Laboratory Program (or approved diagnostic laboratory) will follow the HVTN HIV testing algorithm (as described in the Laboratory Manual of Operations), which is able to distinguish vaccine-induced antibody responses from actual HIV infections.

- All participants can receive HIV-1 diagnostic testing from the site following their last scheduled visit until they are told that they did not receive an HIV vaccine or that they do not have vaccine-induced seropositivity.
- All participants who received vaccine product and who have vaccine-induced positive or indeterminate HIV-1 serology (as measured by the standard anti-HIV antibody screening tests) at or after the study is unblinded will be offered poststudy HIV-1 diagnostic testing (per the HVTN poststudy HIV-1 testing algorithm) periodically and free of charge as medically/socially indicated (approximately every 6 months) unless or until HIV Ab testing is no longer the standard test in clinical settings.

9.8.2 VISP registry

Experimental HIV vaccines may induce Ab production to HIV antigens, producing reactive results on commercially available HIV test kits. This is called "vaccine-induced seropositivity" (VISP). In order to provide poststudy HIV testing to distinguish between VISP and HIV infection, and to mitigate potential social harms resulting from VISP in HIV vaccine recipients who are not infected with HIV, the HVTN has created a VISP registry. Following study unblinding, the registry will allow trained staff to verify that an individual has received an HIV vaccine, and therefore has the potential for VISP. Information in the VISP registry will not be used for research. Rather, the registry exists to support provision of poststudy testing and counseling services to HIV vaccine recipients. The registry contains the names of all study participants, unless they request that their names be removed.

9.9 Contraception status

Contraception status is assessed and documented at every scheduled clinic visit for a participant who was born female and who is sexually active in a way that could cause that participant to become pregnant. Prior to enrollment and throughout the study, staff will ask participants to verbally confirm their use of adequate contraceptive methods. A participant who was born female and is sexually active in a way that could cause that participant to become pregnant should be reminded at all scheduled clinic visits of the importance of using contraception and should be referred to specific counseling, information, and advice as needed. (Specific contraception requirements are listed in Section 7.1). This reminder should be documented in the participant's study record.

Self-reported infertility—including having reached menopause (no menses for 1 year) or having undergone hysterectomy, bilateral oophorectomy, or tubal ligation—must be documented in the participant's study record.

9.10 Urinalysis

Dipstick testing may be performed in the clinic or the lab, as long as the required elements (glucose, protein, and hemoglobin) are tested. The examination is performed on urine obtained by clean catch.

If the screening dipstick is transiently abnormal due to menses or infection, document this issue in the participant's source documentation. For infection, provide appropriate

treatment and/or referral. Following resolution, repeat the dipstick and, if within the eligibility limits specified in the protocol, the participant may be enrolled.

Follow-up urinalysis should be deferred if a participant is menstruating, but should be performed as soon as possible. If a follow-up dipstick is abnormal due to a participant's menstrual period, document in the comment section of the case report form (CRF) and repeat the dipstick once the participant is no longer menstruating. A micro-urinalysis is not required.

9.11 Assessments of reactogenicity

For all participants, baseline assessments are performed before and reactogenicity assessments are performed after each vaccination. All reactogenicity symptoms are graded according to the Division of AIDS Table for Grading the Severity of Adult and Pediatric Adverse Events (DAIDS AE Grading Table), Version 2.0, November 2014, except as noted in Section 11.2.2.

The reactogenicity assessment period is 7 full days following each vaccination per the assessment schedule shown in Table 9-1. Participants will be given a tool on which to record reactogenicity symptoms. Contacts between the participant and the site staff should take place daily during the first 3 days of the assessment period. Participants are instructed to record the resolution date of new or unresolved reactogenicity symptoms present at day 7 to resolution. Participants are instructed to contact the clinic for events that arise during the period between vaccination and the next scheduled visit. In general, a participant who self-reports any postvaccination reaction greater than mild is seen by a clinician within 48 hours after onset, unless the reaction is improving and/or has completely resolved.

Reactogenicity events are reported using CRFs that correspond to the time of assessment in Table 9-1. Reactogenicity assessments include assessments of systemic and local symptoms, vaccine-related lesions, and lymph nodes. Events not listed on a CRF, or with an onset after the reactogenicity assessment period (day of vaccination and 7 full days after), or those meeting SAE/adverse event criteria requiring expedited reporting to DAIDS, are recorded on an adverse experience log form.

Day	Time	Performed by
0 ^a	Baseline: before vaccination	HVTN CRS staff
	Early: 25-60 minutes after vaccination	HVTN CRS staff
	Between early assessment and 11:59pm day 0	HVTN CRS staff or participant
1	Between 12:00am and 11:59pm day 1	HVTN CRS staff or participant
2	Between 12:00am and 11:59pm day 2	HVTN CRS staff or participant
3	Between 12:00am and 11:59pm day 3	HVTN CRS staff or participant
4	Between 12:00am and 11:59pm day 4	HVTN CRS staff or participant
5	Between 12:00am and 11:59pm day 5	HVTN CRS staff or participant
6	Between 12:00am and 11:59pm day 6	HVTN CRS staff or participant
7 ^b	Between 12:00am and 11:59pm day 7	HVTN CRS staff or participant

^a Day of vaccination

^b New or unresolved reactogenicity symptoms present on day 7 are recorded until resolution

9.11.1 Assessment of systemic and local symptoms

Systemic symptoms include increased body temperature, malaise and/or fatigue, myalgia, headache, chills, arthralgia, nausea, and vomiting. Local symptoms include pain and/or

tenderness proximal to the injection site. The daily maximum severity reached for each symptom during the assessment period is reported.

Body temperature is measured by oral or infrared thermometry and reported in degrees Celsius. If temperature is measured in Fahrenheit, the conversion to Celsius should be documented in the participant's chart note. A measurement is taken once daily during the assessment period and should be repeated if participant is feeling feverish.

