Local and general solicited symptoms could be divided into 4 groups given their frequency per dose given into brackets (by decreasing order):

- Pain (between 86.3% and 96.3%) with few grade 3 symptoms (\leq 3.4%).
- Fatigue (between 33.8% and 46.6%), feverishness (between 22.9% and 53.4%), headache (between 35.0% and 48.3%) and myalgia (between 25.8% and 43.3%). Few cases of grade 3 myalgia and fatigue were reported (\leq 4.2%). For feverishness the frequency of grade 3 symptoms was 10.1% and for headache was 5.9% in the gp120/ NefTat/ AS01_B group.
- Redness, swelling, nausea and fever: the frequency of those symptoms did not exceed 30.3%. Few grade 3 nausea and fever were reported ($\leq 2.1\%$). The frequency of grade 3 redness and swelling was 20.2% and 13.9% respectively in the gp120/ NefTat/ AS01_B group.
- Diarrhea and vomiting: the frequency of these symptoms was less than or equal to 7.5%. No grade 3 diarrhea was observed, and only 0.4% of the doses were followed by grade 3 vomiting.

Almost all general symptoms (fatigue, feverishness, headache, myalgia, nausea and fever, vomiting) were considered as related to the vaccination, except for diarrhea.

The duration of general symptoms was less than or equal to 2 days in most cases whereas the duration of local symptoms was often more than 2 days. In the gp120/ NefTat/AS01B group the overall frequency of the general symptoms tended to be higher after the 2nd, 3rd, or 4th dose of vaccine compared to the first dose (but not for all symptoms and all groups).

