6.4.3.1 Reactogenicity

The number and percentage of participants experiencing each type of reactogenicity sign or symptom will be tabulated by severity and treatment group and the percentages displayed graphically by group. For a given sign or symptom, each participant's reactogenicity will be counted once under the maximum severity for all injection visits. In addition, to the individual types of events, the maximum severity of local pain or tenderness, induration or erythema, and of systemic symptoms will be calculated. Kruskal-Wallis tests will be used to test for differences in severity between groups.

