9.11.2 Assessment of injection site

Typical injection site reactions are erythema or redness and induration or swelling. The maximum horizontal and maximum vertical measurements for all injection site reactions are recorded.

All injection site reactions are monitored until resolution. Areas greater than 25 cm^2 are followed daily; otherwise, the frequency of follow-up is based on clinician judgment.

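### The planned reactogenicity tables keep one maximum grade per symptom over all visits, so they do not describe how long reactions last or separate them by dose

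*Combined protocol and SAP*

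**What the plan says.** **Collection.** Section 9.11: "The reactogenicity assessment period is 7 full days following each vaccination per the assessment schedule shown in Table 9-1". The same section counts the vaccination day as well ("day of vaccination and 7 full days after"), so Table 9-1 has eight daily assessments, days 0 to 7. Section 9.11.1 asks for one grade per symptom per day: "The daily maximum severity reached for each symptom during the assessment period is reported". Later follow-up is narrower. Section 9.11 says "Participants are instructed to record the resolution date of new or unresolved reactogenicity symptoms present at day 7 to resolution", and the footnote to Table 9-1 says "New or unresolved reactogenicity symptoms present on day 7 are recorded until resolution". Section 9.11.2 adds "All injection site reactions are monitored until resolution", with daily follow-up required only for areas above 25 cm² and clinician judgment setting the interval otherwise.

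**Analysis.** Section 6.4.3.1 tabulates participants by severity and treatment group. For a given sign or symptom, "each participant's reactogenicity will be counted once under the maximum severity for all injection visits". Composites (pain or tenderness, induration or erythema, systemic symptoms) also use maximum severity, and Kruskal-Wallis tests compare severity between groups.

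**Objective and endpoint.** Primary objective 1 (Section 5.1) covers safety and tolerability. Its reactogenicity endpoint is severe signs and symptoms, counted up to 7 days after each vaccine dose.

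**The concern.** The daily record carries two things that a single maximum removes: how many days a reaction lasted, and which dose it followed. Both bear on tolerability. The protocol itself describes earlier AS01B experience partly by duration. In Section 4.8.3, general symptoms in one earlier trial mostly lasted 2 days or less, "whereas the duration of local symptoms was often more than 2 days". The same section reports that related symptoms in another trial generally resolved within 2 to 3 days, and gives maximum durations of 1 to 2 days for grade 3 solicited reactions in a booster study. The planned outputs could not be set beside those figures.

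The dose matters because the regimens differ in when active protein is given: Months 3 and 6 in groups 1 to 3, and Months 0, 1 and 6 in groups 4 to 7 (Table 3-1). A maximum over all four visits does not say whether a reaction followed a first or a repeat exposure to adjuvanted protein.

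Section 4.1 says regimens will be selected on safety and immunogenicity data, and Section 4.5 presents direct comparison of the regimens' safety profiles as a strength of the design. A difference in persistence between regimens could be missing from the reports used for that purpose.

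**Working it through.** The documents give no figure for duration, so there is none to reproduce. The check has two parts.

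**1. Collected against analysed (from the documents).**
- Daily grades per symptom per vaccination: days 0 to 7 = 8 (Section 9.11, Table 9-1).
- Vaccination visits: 4 (Table 3-1).
- Maximum daily grades per symptom per participant: 8 × 4 = 32.
- Values kept for analysis: 1 (Section 6.4.3.1).

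Consider two participants. One has a Grade 2 symptom for 1 day after one dose. The other has it for 7 days after each of four doses, 7 × 4 = 28 days. Both are counted once, as Grade 2. This example shows what the summary cannot distinguish; it does not predict what will be seen.

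The neighbouring sections do not fill the gap. Section 6.4.3.2 tabulates AEs by maximum severity or strongest relationship. Section 6.4.3.3 concerns laboratory values. Section 6.4.3.4 tabulates discontinuations and early terminations by reason. None gives a duration.

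**2. What might be missed (illustration; inputs assumed except n).**
- n = 50 per arm, the enrolment in groups 2, 3 and 5 to 7 (Section 6.1).
- Share *s* of each arm reaching Grade 2 or above: 50%, equal in both arms.
- Days at Grade 2 or above among those affected: 1 + Poisson(m − 1), where m is the mean, capped at 8.
- Outcome: more than 3 days at Grade 2 or above, with probability s × P(Poisson(m − 1) ≥ 3).
- Test: Fisher's exact, two-sided 0.05, power by exact enumeration.

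For m = 2: 0.50 × 0.080 = 4.0%. For m = 2.5: 0.50 × 0.191 = 9.6%. For m = 3: 0.50 × 0.323 = 16.2%. For m = 4: 0.50 × 0.577 = 28.8%.

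| Mean days, arm A v B | Share reaching Grade 2+ | More than 3 days, A v B | Fisher power |
|---|---|---|---|
| 2 v 2.5 | 50% | 4.0% v 9.6% | 8% |
| 2 v 3 | 50% | 4.0% v 16.2% | 38% |
| 2 v 4 | 50% | 4.0% v 28.8% | 91% |
| 2 v 4 | 25% | 2.0% v 14.4% | 47% |

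A separate simulation used 3,000 replicates and 50 per arm. Maximum grades 0/1/2/3 were assumed at 15/40/35/10% in both arms, and 1 + Poisson days, capped at 8, for anyone with a symptom. Kruskal-Wallis on maximum grade rejected in 4% to 5% of trials whatever the durations. The same test on number of symptom days rejected in 35% (mean 2 v 2.5 days), 78% (2 v 3) and over 99% (2 v 4). The first result follows from giving both arms the same maximum-grade distribution. It restates that a maximum holds no duration information and is not evidence that such a difference is likely.

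**The case against.** The strongest reply is that the analysis matches the endpoint. The endpoint is the occurrence of severe reactions, and a table of participants by maximum grade answers it. Duration is not a named endpoint or objective. This stands: the planned tables are valid and should stay. What remains is that tolerability is in the primary objective, the endpoint is worded per dose, and the data for a fuller description are already being collected.

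Two stronger inferences are tempting, and the documents support neither.
- A reader might infer that duration will never be reported, or that the trial cannot say which regimen gives longer reactions. The protocol refers to a separate HVTN 108 SAP whose text is not in the document reviewed, and Section 6.4 allows for other descriptive analyses. Section 6.4.3.1 does not defer duration to that SAP, but the SAP could add it. The daily grades would exist in any case.
- A reader might infer that regimens with very different tolerability would look identical throughout. Discontinuations are tabulated by reason (Section 6.4.3.4), and the SMB sees cumulative reactogenicity unblinded about every 4 months (Section 11.1.2). These are not duration measures, but they could still differ between regimens.

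Two limits on the data also stand. For graded symptoms, a resolution date is requested only if the symptom is present at day 7, so shorter durations must be derived from the daily grades. For injection site reactions of 25 cm² or less, follow-up intervals are left to the clinician. Finally, the background in Section 4.8.3 describes mostly short reactions and does not support a 2 v 4 day contrast as the expected case.

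**Conclusion.** The point holds as an improvement to the analysis and does not invalidate the primary safety evaluation. In the documents supplied, up to 32 daily grades per symptom become one, and no planned output describes persistence or separates reactions by dose. That conclusion rests on the text alone. The planned tables and Kruskal-Wallis test therefore cannot show a difference in persistence between adjuvants, protein doses or schedules.

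The practical size is uncertain and should be given as a range. Under the stated assumptions, a simple comparison of prolonged Grade 2 or above reactions has power of 8% to 91% as the assumed gap in mean duration goes from 0.5 to 2 days, and 47% at the largest gap if only a quarter of each arm reaches Grade 2. Quoting the 91% alone would mislead. Because small gaps would often go undetected by a formal test, the additions are best presented descriptively.

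**What to change.** Amend Section 6.4.3.1; the collection text in Section 9.11.1 needs no change. Keep the maximum-severity tables and add, by treatment group and dose:
- for each solicited symptom, descriptive summaries of the number of days at Grade 2 or above and at Grade 3 or above, derived from the daily grades;
- the percentage of participants with the symptom still present after day 3 and at day 7;
- time to resolution only for symptoms present at day 7 and for injection site reactions, with a note that reactions of 25 cm² or less are followed at clinician-judged intervals, so their resolution times are interval-observed.

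If the separate SAP already contains such summaries, a cross-reference in Section 6.4.3.1 is enough. The cost is a few extra tables from data that Section 9.11 already requires. No new visits, data collection, sample size or clinical rules are needed.

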9.11.2 Assessment of injection site

Typical injection site reactions are erythema or redness and induration or swelling. The maximum horizontal and maximum vertical measurements for all injection site reactions are recorded.

All injection site reactions are monitored until resolution. Areas greater than 25 cm^2 are followed daily; otherwise, the frequency of follow-up is based on clinician judgment.

9.11.3 Assessment of lymph nodes

This assessment is required only when reactogenicity assessments are performed by HVTN CRS staff, not by the participant.

Only the proximally draining lymph nodes are assessed (eg, axillary nodes on the same side of the body for injections given in the deltoid). Lymph nodes are first evaluated for enlargement and tenderness. If they are found to be enlarged, measurements are taken to determine the size (widest diameter) of the enlarged node(s).

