4.8.1 Clinical studies with DNA-HIV-PT123

HVTN 096/EV04: DNA-HIV-PT123, NYVAC (NYVAC-HIV-PT1 and NYVAC-HIV-PT4), and AIDSVAX B/E are currently being tested in an early phase clinical trial. HVTN 096/EV04 is being conducted exclusively in Lausanne, Switzerland. The HVTN 096/EV04 study design is shown in Table 4-9.

Group	N	Month 0	Month 1	Month 3	Month 6
1	20	NYVAC ¹	NYVAC	NYVAC+ AIDSVAX B/E ³	NYVAC+ AIDSVAX B/E
	4	Placebo ⁴	Placebo	Placebo	Placebo
2	20	NYVAC+ AIDSVAX B/E	NYVAC+ AIDSVAX B/E	NYVAC+ AIDSVAX B/E	NYVAC+ AIDSVAX B/E
	4	Placebo	Placebo	Placebo ⁴	Placebo
3	20	DNA ²	DNA	NYVAC+ AIDSVAX B/E	NYVAC+ AIDSVAX B/E
	4	Placebo	Placebo	Placebo ⁴	Placebo
4	20	DNA+ AIDSVAX B/E	DNA+ AIDSVAX B/E	NYVAC+ AIDSVAX B/E	NYVAC+ AIDSVAX B/E
	4	Placebo	Placebo	Placebo ⁴	Placebo
Total	80/16				

Table 4-9 Study design of HVTN 096/EV04

¹NYVAC: NYVAC-HIV-PT1 and NYVAC-HIV-PT4 containing clade C ZM96 gp140 and ZM96 gag- CN54 pol-nef respectively, each delivered at a dose of $\geq 5x106$ plaque-forming units (PFU), administered IM. ²DNA: DNA-HIV-PT123 containing clade C ZM96 gag and gp140, CN54 pol-nef, delivered at a dose of 4 mg, administered IM.

³AIDSVAX B/E: 300mcg of subtype B (MN) HIV gp120 glycoprotein and 300mcg of subtype E (A244) HIV gp120 glycoprotein absorbed onto 600mcg of aluminum hydroxide gel adjuvant, administered IM. ⁴Placebo: Sodium Chloride for injection, 0.9% administered IM.

HVTN096/EV04 completed accrual of 96 participants in April, 2013. As of October 31st, 2014 there have been no SAEs reported that were deemed related to the study products. There was 1 death by cranial trauma in a motorcycle accident. In studies where these vaccines and other similar vaccines were given, the most common complaints have been injection site pain/itching, mvalgia/arthralgia, headache, and malaise/fatigue. Most of these reactions have been mild to moderate. By October, 2013, all participants had completed the vaccine regimens in HVTN 096/EV04, and the most common complaints have been mild or moderate malaise/fatigue, myalgia, headache and injection site pain. The most common AE deemed by the site investigator to be related to study product was lymphadenopathy (n=9, 9.4%).

Interim immunogenicity data analysis has shown that the DNA prime/NYVAC-AIDSVAX boost regimen induces higher number of responders and greater magnitude of both CD4 and CD8 T-cell responses. In particular, CD4+ T cell response rates and

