^f For a participant who was born female (ie, assigned female sex at birth), pregnancy test must be performed on urine or blood specimens on the day of vaccination with negative results received prior to vaccination. Pregnancy test to determine eligibility may be performed at screening, but must also be done on Day 0 prior to vaccination. Persons who have undergone total hysterectomy or bilateral oophorectomy (verified by medical records), are not required to undergo pregnancy testing.

^g Pregnancy testing at the indicated visit is only required of participants who are born female and are providing a cervical and/or rectal secretion sample.

^h Syphilis testing by serology and Chlamydia and gonorrhea testing by urine or swab will only be performed if the participant agrees to provide a mucosal sample.

HVTN 108, Version 2.0 / August 8, 2016

Bacterial vaginosis (cervical/vaginal swab) ⁱ	_	Х	_	_	_	_	_	_	_	Х	_	Х	
Yeast, if indicated (cervical/vaginal swab) ⁱ	_	Х	_	_	_	_		_	_	Х	_	Х	
Pap smear ⁱ	Х	_	_	_	_	_	_	_	_	_	_	_	_
Mucosal secretion collection (optional) ^k													
Cervical, rectal, semen	—	Х	—	—	—	—		—	—	Х	—	Х	_
Vaccination procedures													
Vaccination ¹	_	Х		Х	_	Х	_	Х	_	_			
Reactogenicity assessments ^m	_	Х	_	Х	_	Х		Х	Х	_	_	_	
Poststudy													
Unblind participant			_	_	_			_					Х

¹ Cervical/vaginal swabs will only be collected from participants who agree to provide a cervical secretion sample; and, testing for Trichomonas vaginalis, bacterial vaginosis, and (if clinically indicated) yeast.

^j Only for volunteers born female who consent to provide cervical secretion samples, per Sections 7.1 and 9.6. If collection of a pap smear is required, this may be done at any time provided the results are available prior to the collection of the cervical secretion samples.

^k Optional mucosal specimens must be collected prior to first vaccination once the participant has been found to have met mucosal specimen collection criteria specified in in section 9.6.

¹Blood draws required at vaccination visits must be performed prior to vaccination; however, it is not necessary to have results prior to vaccination, except for results of a urine or serum pregnancy test, if indicated.

^m Reactogenicity assessments performed or recorded in the postvaccination symptom log for at least 7 days postvaccination (see Section 9.11).

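### After doses 1-3 no lymph node assessment is required between 60 minutes and day 7, so node findings may be ascertained unequally across arms

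*Combined protocol and SAP*

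**What the plan says.** Section 9.11 of the protocol defines the content of reactogenicity: "Reactogenicity assessments include assessments of systemic and local symptoms, vaccine-related lesions, and lymph nodes". The window is the day of vaccination and 7 full days after it. Section 9.11.3 then limits the node component: "This assessment is required only when reactogenicity assessments are performed by HVTN CRS staff, not by the participant".

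Table 9-1 has two rows reserved to site staff, the pre-dose baseline and "Early: 25-60 minutes after vaccination". Every later row, from the rest of day 0 to day 7 (for example "Between 12:00am and 11:59pm day 1"), may be done by staff or by the participant. Section 9.11 also says: "Contacts between the participant and the site staff should take place daily during the first 3 days of the assessment period". It does not say that these contacts are in person.

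Appendix H marks reactogenicity assessments at the four vaccination visits and at D175. Its footnote reads: "Reactogenicity assessments performed or recorded in the postvaccination symptom log for at least 7 days postvaccination". D14, D42 and D98 carry no such mark. Under Section 9.4 the abbreviated examination at those visits is directed by symptoms.

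The written trigger for an extra visit is: "In general, a participant who self-reports any postvaccination reaction greater than mild is seen by a clinician within 48 hours after onset". The sentence goes on to waive this when the reaction is improving or has resolved.

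**The concern.** The plan counts nodes as reactogenicity but, after three of the four doses, requires nobody to look at them during the days when a nodal response would be expected to develop. An examination within an hour of injection is unlikely to show one.

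What fills the gap is not the same for everyone. A participant who reports a moderate reaction is generally seen by a clinician and may have the nodes examined. A participant with a mild reaction, or none, need not be seen. If arms differ in how often reactions exceed mild, they will differ in how often nodes are examined. A by-arm table of node findings would then mix true differences with differences in looking. Blinding does not prevent this, because the trigger is the reaction itself.

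The plan regards lymphadenopathy as a real possibility. Table 4-11 lists it among the less common risks, and Section 4.8.1 reports it as the most common related AE in HVTN 096/EV04.

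**Working it through.** **1. The schedule.** Days from each dose to the next clinic visit, from Appendices G and H:

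| Dose | Dose day | Next visit | Gap | Reactogenicity mark at that visit |
|---|---|---|---|---|
| 1 | D0 | D14 | 14 days | No |
| 2 | D28 | D42 | 14 days | No |
| 3 | D84 | D98 | 14 days | No |
| 4 | D168 | D175 | 7 days | Yes |

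Only dose 4 has a scheduled clinic assessment inside the window after the 25-60 minute one. The pre-dose baseline assessments in Section 9.3 do not fill the gap. They fall 28, 56 and 84 days after doses 1, 2 and 3 (28 − 0, 84 − 28, 168 − 84).

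**2. How many visits this covers.** Group sizes and products are from Table 3-1.

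- All vaccination visits: 334 × 4 = 1,336. Doses 1-3: 334 × 3 = 1,002, or 75%.
- Of those 1,002, all-saline visits number 180 (groups 4-7 at Month 3) + 24 × 3 = 72 (group 8) = 252. The remaining 750 include an active product.
- Adjuvanted-protein visits: groups 1-3, (30 + 50 + 50) × 2 = 260; groups 4-7, (30 + 50 + 50 + 50) × 3 = 540; total 800.
- Followed by D175 (Month 6 dose): 130 + 180 = 310. Not followed by it: 800 − 310 = 490, and 490/800 = 61%.
- Scheduled coverage of protein visits also differs by schedule: 130/260 = 50% in groups 1-3 and 180/540 = 33% in groups 4-7.

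**3. What incomplete ascertainment does to the plan's safety figures.** Nothing in the plan is sized on nodes. The nearest figure is Table 6-1, which takes every event as observed. At a true rate of 10% and n = 50, Pr(0) = 0.9^50 = 0.0052, Pr(1+) = 0.9948 and Pr(2+) = 0.9662. These agree with the stated 0.005, 0.99 and 0.97.

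Now let observed rate = true rate × probability of detection. The detection probabilities below are assumptions, since the documents give none, and the illustration leaves D175 aside. With the same 10% true rate in both arms:

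- detection 50%: observed rate 5%, expected cases 2.5 per 50, Pr(1+) = 0.923;
- detection 10%: observed rate 1%, expected cases 0.5 per 50, Pr(1+) = 0.395.

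The apparent ratio is 0.50/0.10 = 5 with no true difference. The true rate cancels, so the ratio depends only on the two detection probabilities. For assumed pairs of 30%/5%, 50%/10%, 70%/10% and 70%/30% it is 6, 5, 7 and 2.3. With equal detection it is 1. This shows the mechanism and is not an estimate for this trial.

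**4. The earlier-trial rate.** In HVTN 096/EV04, 9/96 = 9.4%. Table 4-9 shows that 40 of the 96 received DNA (groups 3 and 4), 40 received vaccine without DNA, and 16 received placebo. Every vaccinee was also assigned NYVAC and AIDSVAX B/E. The nine cases are not split by arm.

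**The case against.** The strongest reply is that nodes are not left unwatched. Section 9.11 tells participants to contact the clinic about events between visits. Section 9.4 has staff ask about new AEs at every follow-up visit, including D14, D42 and D98. Section 11.2.2 collects unsolicited AEs for 30 days after each vaccination visit. Table 9-1 allows staff assessment on any day. A reader might infer that a node is found only if some other reaction is reported, or that nodes go almost unrecorded after doses 1-3. The documents do not support either reading, because a participant can report the node itself. What remains is that this route is unprompted, whereas the other reactogenicity signs are solicited daily.

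A reader might also infer that the AS01B arms are known to be more reactogenic than the MF59 arms, so that the direction of bias is settled. The documents give no such comparison. Section 4.8.3 compares AS01 with unadjuvanted antigen, using a different antigen. It also reports no difference between groups in the proportion of doses followed by related symptoms across AS01B and two AS02 formulations. Differential detection is a reasonable inference, but it has not been shown.

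It is equally tempting to take 9.4% as the expected rate for this DNA product. Step 4 shows why it cannot serve. HVTN 092 and HVTN 105 used the same DNA, and Section 4.8.1 does not list lymphadenopathy among their most common complaints.

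Finally, D175 gives every arm a fixed day-7 assessment, after a dose at which all seven vaccine groups receive adjuvanted protein. That stands, and the fix builds on it.

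**Conclusion.** The point holds as a gap in ascertainment. After doses 1-3 no staff node assessment is required between 60 minutes and day 7. The gap covers 75% of all planned vaccination visits and 61% of adjuvanted-protein visits. In-window findings after those doses come from unprompted self-report or from visits triggered by a reaction greater than mild, so ascertainment may differ by arm if reactogenicity does. The size and direction of any bias cannot be derived, because the documents give neither the rate of such reactions by arm nor the rate of node examination.

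This rests on three assumptions: the D175 mark means an assessment by staff on or near day 7 (visit windows are in the Study Specific Procedures); the symptom log, which is not reproduced, has no node item, as Section 9.11.3 implies; and the daily contacts need not be in person.

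The consequence is modest. Nodes are not in the Section 5.1 list of solicited signs, and Section 6.4.3.2 plans no formal testing of AEs. What is exposed is any by-arm display of node findings. Section 6.4.3.1 counts each sign once per participant, at its maximum over all injection visits. If nodes are handled that way, the uniform D175 findings will be pooled with triggered ones.

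**What to change.** 1. Add one item to the existing 7-day log for all participants: *swollen or tender glands in the armpit, left/right*. The side is informative because DNA or its placebo goes in the left deltoid and protein or its placebo in the right. Report these self-reports separately from staff findings.
2. Tabulate staff node findings by dose, with the number examined as denominator, instead of only as a maximum over all visits.
3. Name the D175 assessment as the main between-arm comparison of nodes. State that it applies to those who received dose 4, and that a single look at day 7 misses nodes that have already settled.
4. Optionally, make axillary palpation a fixed item of the abbreviated examination at D14, D42 and D98. This is 14 days after the dose and outside the 7-day window, so it supplements the log item and cannot replace it.

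The cost is one log line and a change to the table shells, with no new visits or staff. The optional palpation adds about a minute at existing visits. The downside is more mild, self-reported node findings, including in placebo recipients, but they would be solicited alike in every arm.
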